Testing consists of two parts: A battery of cognitive and psychosocial assessments and an assessment of physical variables. The following paragraphs demonstrate the different methods and measures that will be used in the project.

An endurance test (ventilatory threshold/ VO_{2max}) will be given. There will be strength and agility exercises as used by the KAN study (The Norwegian Directorate of Health/Norwegian School of Sport Science)³: Push-ups and the Stork Balance Test. The push-up test is a maximal test where the participants perform a maximum number of correct push-ups. The balance test is a timed test where the goal is to keep one's balance as long as possible.

Ventilatory threshold test: This test is performed on a treadmill. The participant starts without warming up on the starting load after being explained the test procedure and how to record the rating of perceived exertion (RPE) (Borg, 1970): stage duration 1 min, start load 6 km/h, gradient angle 5 %. Increase in load: 1 km/h. Oxygen uptake and heart rate are continuously measured during the test at 10 s intervals with the help of a metabolic cart, MetaMax II (Cortex Biophysik GmbH, Germany) and a Polar heart rate monitor (Polar OY, Kempele, Finland).

Strength and agility tests: Push-ups with a straight body, from chest touching the floor to fully extended arms. The Stork Balance Test involves keeping one's balance on one leg for as long as possible; once with open and once with closed eyes. These tests are chosen because of ease of administration and the availability of such data for comparison.

Test equipment: Treadmill: Sole Incline TT8
 Metabolic analyzer: Cortex MetaMax II
 Software: Cortex MetaSoft 1.11.05
 RPE: Borg RPE scale (1970)

The change in endurance fitness will be evaluated on the basis of the VO_{2max} , where workload at threshold point will quantify the endurance capacity. The change in the number of push-ups and the balancing time will be used for the strength/agility measures.

The study will investigate changes in satisfaction with life, executive functions and psychological distress over a period of 12 months. A battery of cognitive and psychosocial assessments will be used (a modified version of the one used in the "Executive functions in patients with substance use disorders: effects on the course of treatment" project (Stayer study)⁴):

- National Quality Register⁵
- AUDIT-E - Alcohol Use Disorders Identification Test (Extended)

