- DUDIT-E - Drug Use Disorders Identification Test (Extended)
- Symptom Checklist-90-R (SCL-90-R)
- Satisfaction With Life Scale (SWLS)
- Pittsburgh Sleep Quality Index (PSQI)
- Connors Continuous Performance Test (CPT 3)
- Behavior Rating Inventory of Executive Function - Adult Version (BRIEF-A)
- Iowa Gambling Task (IGT)
- Biweekly status update on outcome goals

Executive functions will be assessed by the Behaviour Rating Inventory of Executive Function-Adult self-report version (BRIEF-A), psychological distress by the Symptom Checklist-90-R (SCL-90-R), and satisfaction with life by the Satisfaction With Life Scale (SWLS). Substance use will be assessed

³ *Kartlegging av fysisk aktivitetsnivå, helse relatert fysisk form og determinanter for fysisk aktivitet hos voksne og eldre i Norge* (Survey of physical activity, health-related physical form and determinants of physical activity among adults and elderly in Norway).

⁴ The Stayer study is a prospective longitudinal cohort study of a group of SUD patients who started a new in-patient or out-patient treatment sequence for SUD, within the area of the local health authority Stavanger University Hospital.

⁵ National Quality Register for the treatment of harmful use of/addiction to drugs

by self-reports on the Alcohol Use Disorders Identification Test (AUDIT-E) and the Drug Use Disorders Identification Test (DUDIT-E). Changes in test scores will be used to quantify the development of the mental aspects of health.

The first meeting will be between a potential participant and the project organizer. In this meeting, the project organizer will inform about the study and go thoroughly through the consent form. The participant will then sign a written consent about voluntary participation in the study.

Next, a baseline assessment will take place. The participant and the project organizer will meet at the organizer's office to complete the battery of cognitive and psychosocial assessments. Afterwards, they will meet at the test lab at Solli Hospital in order to execute the physical tests.

After testing is completed, the participant will be informed whether they are part of the intervention or the control group. The organizer will call a colleague who keeps a list generated by the approved randomization program "Random Allocation Software 2.0" (Saghaei, 2004) securely locked away. The project organizer does not have any knowledge about the order and can thus not influence the randomization process.

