Participants in the intervention group will start with the introductory meeting. The introductory meeting will enable the participants and training contact to get to know each other. Good personal chemistry is important, as they will spend much time together in the coming months. It is useful to note down interests, training ambitions and self-evaluated physical fitness level at this meeting, as this will help in the planning of the training. Training with a training contact is the primary intervention. Concerning the practical procedure, training contact and participant will meet for three hours a week⁶ (in either two or three sessions) for 12 weeks. The training contact will motivate and guide the participants. One goal is to enable the participants to conduct training alone by the end of the project. Training content can be chosen by the participant (to increase the likelihood of study completion) but should be feasible and consist of a combination of aerobic and muscle-strengthening activity. Training intensity should be increased gradually, to avoid injuries and create motivation. All training sessions will be recorded in a diary, where the type of exercise, time, intensity and other remarks are noted. Both the participant and training contact should make such recordings to make the documentation as complete as possible.

After the 12 weeks intervention period another testing will be conducted. This post-measurement will include the same tests as those performed at the baseline measurement.

Participants who were selected into the control group are on a waiting list for 12 weeks and receive treatment as usual. After three months they will go through the assessment procedure again. Subsequently, they will receive the same intervention as the original intervention group. They, too, will get a training contact for 12 weeks and will be tested afterwards.

As a follow-up, all participants will be assessed 12 months after baseline measurement. It is important that the post-measurement tests are carried out identically to those at pre-measurement, in order to obtain a valid result.

All sensitive data (digital and non-digital) generated is confidential and will be treated according to the standards set by the Norwegian Data Inspectorate (*Datatilsynet*) and in compliance with the Health Research Act and the Personal Data Act.

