Data generated in this project will mostly be on interval or ratio level (whether the rating of perceived exertion is ordinal or interval data will not be discussed here). To express group results, the mean will serve as a measure of the central tendency, with the standard deviation expressing the spread of results within the group. If useful, the standard error of the mean (SEM) will be used to express

⁶ Based on the WHO's recommended levels of physical activity for adults aged 18 - 64 years (http://www.who.int/dietphysicalactivity/factsheet_adults/en/)

the accuracy of the mean value. If results are highly skewed (skewness > 1.5), a log transformation and geometric mean will be used together with a 95% confidence interval to express central and spread tendencies. To compare results over time, an ANOVA/t-test of repeated measures will be performed with a Sidak/Holmes post hoc test. Group comparisons will be made with an ANOVA/t-test for independent groups. If the test of normality should fail (Kolmogorov-Smirnov with Lilliefors correction), the corresponding non-parametric tests will be used, i.e. the Wilcoxon-Mann-Whitney Rank Sum Test for independent t-tests and ANOVA on rank for repeated measures (Tukey post hoc). Level for statistical significance will be set at the traditional $p \leq 0.05$. Effect sizes will be calculated according to Cohen (1988) with the help of an online effect size calculator (the CEM effect size calculator, Centre for Evaluation and Monitoring, Durham University, Durham, United Kingdom: <http://www.cemcentre.org/evidence-based-education/effect-size-calculator>). An effect size of ≥ 0.5 will be considered clinically relevant (two-sided). If there is a need for building indexes of different types of scores, Z-scores will be used. The statistical power of 0.8 can be reached with at least 10 subjects in two groups, based on previously published data on fitness development and depression score. Target recruitment is nonetheless set higher than this with $n = 30$ in each group.

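### The between-group test has no baseline covariate; adjusting for the baseline score already collected would usually be more precise for roughly normal outcomes

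*Protocol*

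**What the plan says.** All the relevant text is in Protocol section 4.1.

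- **Test between groups:** "Group comparisons will be made with an ANOVA/t-test for independent groups". No covariate is named.
- **Fallback:** "If the test of normality should fail (Kolmogorov-Smirnov with Lilliefors correction), the corresponding non-parametric tests will be used". For two independent groups the named fallback is the Wilcoxon-Mann-Whitney test.
- **Baseline is available:** participants complete baseline testing before they learn their arm. Of the 12-week visit the protocol says: "This post-measurement will include the same tests as those performed at the baseline measurement".
- **Outcomes are worded as changes:** "Changes in test scores will be used to quantify the development of the mental aspects of health" and, for the strength and balance tests, "The change in the number of push-ups and the balancing time will be used for the strength/agility measures". Endurance is likewise described as a change.
- **Size and threshold:** 30 per group are planned, significance is at 0.05, and a two-sided standardised effect of at least 0.5 counts as clinically relevant.

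No statistical analysis plan is at hand. The point is raised because the protocol itself fixes the test.

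**The concern.** The 12-week comparison is the randomised one, because the control group then receives the intervention. For each re-tested outcome the trial will hold a baseline value that allocation cannot have influenced. An independent-groups test on change scores uses that value with a fixed coefficient of 1. ANCOVA estimates the coefficient, and for roughly normal scores this removes more residual variance at any ordinary pre-post correlation.

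Precision is at stake. The protocol plans 30 per arm, names drop-out as a particular worry at this size, and does not expect many more than 60-80 completers. Power at its own relevance threshold is therefore limited at low to moderate correlations, and a covariate already in the data set is an inexpensive way to improve it.

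**Working it through.** **The protocol's own power figure.** It says power 0.8 can be reached with at least 10 subjects in two groups, but gives no effect size or SD, so the figure cannot be recomputed. Solving back with the noncentral t gives an implied effect of 1.32 SD if 10 per group is meant, or 2.02 SD if 10 in total. The figure does not bear on the choice of model, so the comparison below uses the protocol's 0.5 threshold.

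**Inputs**
- From the protocol: n = 30 per arm, two-sided 0.05, effect d = 0.5.
- Assumed: the true effect is 0.5 of the raw-score SD, the SD is equal at both visits, scores are roughly normal, all 30 per arm complete, and the pre-post correlation r lies between 0.3 and 0.9.

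**Variance of the group difference, relative to comparing 12-week scores alone**
- Change scores: 2(1 - r), with 2n - 2 = 58 degrees of freedom.
- ANCOVA: (1 - r²)(1 + T²/(2n - 2)), with 2n - 3 = 57 degrees of freedom. T is the chance baseline t-statistic, and power is averaged over its distribution. The mean of the imbalance factor is 1 + 1/(2n - 4) = 1 + 1/56 = 1.018.

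**Power** comes from the noncentral t with noncentrality d√(n/2) / √(variance factor).

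Example at r = 0.5:
- Change score: the factor is 2(1 - 0.5) = 1, the noncentrality is 0.5 × √15 = 1.936, and power is 0.478.
- ANCOVA: the factor before imbalance is 1 - 0.25 = 0.75, the noncentrality is 1.936/√0.75 = 2.236, and power is 0.594. Averaged over chance imbalance it is 0.587.

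| r | Change score, 30/arm | ANCOVA, 30/arm | Gain (points) | Change score, 40/arm | ANCOVA, 40/arm |
|---|---|---|---|---|---|
| 0.3 | 36% | 51% | 14 | 46% | 63% |
| 0.5 | 48% | 59% | 11 | 60% | 72% |
| 0.7 | 69% | 75% | 6 | 81% | 87% |
| 0.8 | 85% | 88% | 3 | 94% | 96% |
| 0.9 | 98.9% | 99.1% | 0.2 | 99.85% | 99.89% |

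Gains are taken from unrounded powers. The 40-per-arm columns are the upper end of the 60-80 completers mentioned in section 4.1.

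**Where ANCOVA stops gaining (30 per arm)**
- Against change scores the variance ratio is (1 + r)/2 × 57/56. It equals 1 at r = 112/57 - 1 = 0.965.
- Against 12-week scores alone the ratio is (1 - r²) × 57/56. It equals 1 at r = √(1/57) = 0.132.
- Beyond either limit the variance penalty is at most about 1.8%.

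**Non-normal scores.** The planned rule (t-test, or rank test if normality fails in either arm) was simulated with 30 per arm and 20,000 trials per cell. Baseline and 12-week scores were gamma-shaped with a shared component, and treatment added a constant shift. With raw-score skewness 1.5, the rule on change scores has power 42, 59, 88 and 98% at r = 0.3, 0.5, 0.7 and 0.8. ANCOVA used throughout has 52, 61, 77 and 88%. ANCOVA therefore gains at r of 0.5 or less and loses up to about 12 points above that. If 12-week scores are compared instead, the rule has 62% against 52% for ANCOVA at r = 0.3.

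**The case against.** **The planned test is valid and already uses baseline.** This stands. Randomisation protects the t-test, and subtraction brings baseline in. At r of 0.7 or more the gain is only 6 points or fewer, and the protocol gives no r. Much larger gains (27, 40 and 51 points at r = 0.7, 0.8 and 0.9) arise only if 12-week scores are compared without subtraction. The wording about changes makes that the less likely reading, so those figures should not carry the point.

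**The model form could be left to an analysis plan.** In general, yes. Here, however, the protocol names the test, the trigger and the fallback, so the suggestion is directed at text that exists.

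**ANCOVA can lose to the rank test.** This also stands, as the simulation shows. It is a reason not to replace the fallback outright.

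**A stronger reading.** A reader might infer that the normality-triggered switch is itself a defect, because it lets the data choose between a mean difference and a rank comparison that address different quantities. The evidence does not support this:
- The rule is set in advance, and its simulated type I error is 0.045-0.058.
- In the skewed cases simulated, the rank test was significant while the confidence interval for the mean difference included zero in 2-18% of trials. But the change scores in that model are symmetric and heavy-tailed (skewness about 0, excess kurtosis about 1.0-5.6), and the mean difference and the rank-based shift both average 0.50. The discordance therefore reflects the rank test's greater efficiency.
- The rule "If results are highly skewed (skewness > 1.5), a log transformation and geometric mean will be used" is worded as a way to describe centre and spread. It does not set the test.

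**Conclusion.** The point holds as an optional improvement in precision. Where the plan would use the independent-groups t-test or ANOVA on roughly normal outcomes, adjusting for the baseline score is more precise than change scores for any r below about 0.96. At 30 completers per arm and a true effect of 0.5 SD this is worth about 11-14 points of power at r of 0.3-0.5, 3-6 points at 0.7-0.8, and almost nothing at 0.9. The size rests on r, the equal SDs and the effect, all of which are assumed.

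It does not follow that the planned analysis is biased, that it inflates type I error, or that the rank fallback must go.

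**What to change.** In the statistical paragraph of section 4.1, for each outcome measured at baseline:

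1. Where the independent-groups t-test or ANOVA would apply at 12 weeks, regress the 12-week score on arm and the baseline value of the same score.
2. Report the adjusted mean difference with its 95% confidence interval, and a standardised effect (adjusted difference divided by the baseline SD) to read against 0.5.
3. Keep the Wilcoxon-Mann-Whitney test for outcomes that clearly depart from normality, or as a sensitivity analysis.

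The cost is a few sentences and one degree of freedom, with no new measurement. The variance penalty is at most about 1.8%, at very low or very high r. If ANCOVA were also used in place of the rank test, it could have less power for heavy-tailed change scores or skewed 12-week scores, which is why step 3 keeps the rank test.

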4.1 Study design, choice of methodology and analysis

The number of participants is estimated at 60, recruited from OST-facilities within the Helse Bergen area. To be eligible for admission to the study, participants must (a) sign a written informed consent to participate in the project, (b) be participating in the LAR²-program, (c) be on a steady fixed dose of medication and (d) be at least 18 years of age. Exclusion criteria are pregnancy in women and having joined the LAR-program for less than three months ago. Enrolment in the project will be a consecutive process until the required number of participants is recruited. Participants will be randomly selected for the intervention group or the control group. The intervention group will be given their training contacts (Skrede, Munkvold, Watne, & Martinsen, 2006). Together they will decide on a training schedule that suits the individual with regard to frequency, amount and type of training. Central aspects are user involvement and individual adaptation. All training programs have in common that they include endurance and strength exercises and that the intensity will increase during the intervention period. A representative group, who will not be given an intervention, serves as the control group. The project organizer/PhD candidate will be in touch frequently with members of the control group in order to keep them motivated to stay on the waiting list and to offer social contact. The participants will also answer a Likert scale question that documents the amount of physical activity and drug use the past fortnight.

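### The test stated for the 12-week group comparison allows neither for unequal variances nor for shared training contacts, so its type I error could depart from the stated 0.05

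*Protocol*

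**What the plan says.** All of this is in Protocol section 4.1.

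- **Test.** "Group comparisons will be made with an ANOVA/t-test for independent groups". If a normality test fails, "the corresponding non-parametric tests will be used, i.e. the Wilcoxon-Mann-Whitney Rank Sum Test for independent t-tests". Marked skewness leads to a log transformation. No version for unequal variances and no term for the training contact is named.
- **Level and size.** "Level for statistical significance will be set at the traditional" 0.05. The planned size is 30 per group, 60 in all.
- **Trained arm.** "Training with a training contact is the primary intervention". The contact motivates and guides for three hours a week over 12 weeks. On the content: "Together they will decide on a training schedule that suits the individual with regard to frequency, amount and type of training".
- **Control arm.** Controls wait 12 weeks without a contact. They then receive the same 12-week intervention, with a contact. Everyone is assessed again 12 months after baseline.
- **Not stated.** The number of contacts, how many participants each one serves, and an expected drop-out rate.

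**The concern.** An independent-groups ANOVA, or a pooled t-test, takes the two arms to have equal variance and every participant to be independent of every other. Up to week 12 the intervention gives reason to doubt both, and in one arm only.

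People who train in different amounts and ways may respond more variably than people who wait. The contact may also affect outcome: the protocol itself says in section 4.1 that results might come from the social element, and that feedback from contacts may raise confidence and then performance. If one contact serves several people, their outcomes may move together.

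The stated fallbacks do not help. They are triggered by skewness or non-normality, not by unequal spread or correlation. The rank-sum test also assumes independent observations and, read as a test of a shift in location, equal spread. What is at stake is the standard error and p-value of the one randomised comparison in which controls have not yet been trained.

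**Working it through.** **Inputs from the protocol:** two-sided level 0.05; 30 per arm; contacts in the trained arm only up to week 12.

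**Assumed, because the protocol gives no figure:** ratio of trained to control SD (1 to 2); completers per arm (20 v 30 or 30 v 20, as examples); participants per contact, m (1 to 10); intraclass correlation within contact, ICC (0.05 to 0.10). The control SD is set to 1.

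**Step 1, the stated level.** With 30 v 30, equal SDs and no sharing, simulation (60,000 null trials per scenario, Monte Carlo error about 0.001) gives 0.050, as the protocol intends.

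**Step 2, unequal variance only.** The pooled test uses V_pooled = s_p² (1/n1 + 1/n2), with s_p² = [(n1−1)SD1² + (n2−1)SD2²]/(n1+n2−2). The true variance is V_true = SD1²/n1 + SD2²/n2. For a trained SD of 1.5:

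- 30 v 30: s_p² = (2.25 + 1)/2 = 1.625. V_pooled = 1.625 × 2/30 = 0.1083 and V_true = 3.25/30 = 0.1083. The ratio of standard errors is 1.
- 20 v 30: s_p² = (19 × 2.25 + 29)/48 = 1.495. V_pooled = 1.495/12 = 0.1246 and V_true = 0.1125 + 0.0333 = 0.1458. The ratio is √(0.1246/0.1458) = 0.92, so the standard error is about 8% too small.
- 30 v 20: s_p² = (29 × 2.25 + 19)/48 = 1.755. V_pooled = 1.755/12 = 0.1463 and V_true = 0.075 + 0.05 = 0.125. The ratio is √(0.1463/0.125) = 1.08, so the standard error is about 8% too large.

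Simulated type I error:

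| Trained v control completers | SD ratio | Pooled | Welch |
|---|---|---|---|
| 30 v 30 | 1.5 | 0.051 | 0.050 |
| 30 v 30 | 2 | 0.050 | 0.048 |
| 20 v 30 | 1.5 | 0.071 | 0.051 |
| 20 v 30 | 2 | 0.084 | 0.051 |
| 30 v 20 | 1.5 | 0.035 | 0.051 |
| 30 v 20 | 2 | 0.030 | 0.050 |

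**Step 3, shared contacts only (30 v 30, equal SDs).** The variance of the trained mean is multiplied by D = 1 + (m−1)ICC and that of the control mean by 1. The true standard error is therefore about √[(D+1)/2] times the one the test uses.

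| m | ICC | D | √[(D+1)/2] | Simulated type I error |
|---|---|---|---|---|
| 1 | any | 1.0 | 1.00 | 0.049 to 0.050 |
| 3 | 0.05 | 1.1 | 1.02 | 0.054 |
| 3 | 0.10 | 1.2 | 1.05 | 0.062 |
| 5 | 0.05 | 1.2 | 1.05 | 0.063 |
| 5 | 0.10 | 1.4 | 1.10 | 0.074 |
| 10 | 0.10 | 1.9 | 1.20 | 0.107 |

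**Step 4, what each remedy repairs.** Welch restores about 0.05 in both directions of Step 2 but does not repair sharing: at m = 5 and ICC 0.10 it still gives 0.073. In a separate simulation, a test on contact means in the trained arm with Satterthwaite degrees of freedom gave 0.052 and 0.053 with six contacts of five (ICC 0.05 and 0.10), and 0.064 with three contacts of ten (ICC 0.10). That is a simple stand-in for a partially nested model, not the model itself.

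**The case against.** **The variance problem is absent under the planned design.** This stands at 30 v 30. It needs unequal completion as well, and the direction is unknown. The protocol's extra retention measures are for controls. That may mean that loss was feared there, or that loss will be lower there. If the control arm ends smaller and the trained arm is more variable, the pooled test is conservative.

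**The protocol does not say that contacts are shared.** This stands. Much of the wording reads as one contact with one participant, and the budget in section 4.3 is costed per participant. One sentence on the introductory meeting pairs several participants with a single contact. None of this settles the caseload. With one participant per contact there is no correlation of this kind.

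**If training affects nobody, neither mechanism exists.** This stands too. Individual randomisation then keeps the test valid. The figures apply to a null of zero average effect with effects that differ between people or contacts.

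**The choice of variance form and a contact term belongs to an analysis plan.** This stands in part. A t-test for independent groups could be run in Welch's form, and an analysis plan not seen here may say so. But the protocol names its test and its fallbacks, and none addresses correlation. A later plan can model contacts only if they were recorded. The diary items listed in section 4.1 (type of exercise, time, intensity, remarks) do not name the contact.

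**Conclusion.** The point holds in conditional form. For the 12-week comparison, the stated test and its fallback allow neither for unequal variances nor for correlation within shared contacts, and both are plausible in the trained arm.

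On the assumed inputs, with a trained SD 1.5 times the control SD, type I error is about 7% at 20 v 30 and about 3.5% at 30 v 20. With five participants per contact and ICC 0.05 to 0.10 it is about 6% to 7%. It stays at 5% with one participant per contact, and at about 5% when only the variances differ at 30 v 30.

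A reader might infer more than this:

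- **That the trial's p-values will be too small.** Caseload, ICC, SD ratio and drop-out by arm are all absent from the protocol, and one plausible pattern makes the test conservative.
- **That type I error will be near 10%.** That figure needs three contacts with ten people each and ICC 0.10, for which the text gives no support.
- **That the one-arm asymmetry extends to 12 months.** After week 12 the controls also receive contacts.

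**What to change.** 1. For the 12-week comparison, replace the pooled test with Welch's test, or a regression with heteroscedasticity-robust standard errors. This costs almost nothing when variances are equal and holds the level whichever arm loses more participants.
2. State how many contacts there are and how many participants each serves, and record a contact code for each participant. This is one data field. Include controls once they start training, since both arms have had contacts by 12 months.
3. If any contact serves more than one participant, fit a contact effect in the trained arm only at week 12: a partially nested model with small-sample (for example Satterthwaite) degrees of freedom. If none does, omit the term.

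The downside of step 3 is wider intervals when few contacts are shared. Six contacts leave about 6 − 1 = 5 degrees of freedom for the contact component, and three leave 2. With about three contacts the correction also remains slightly liberal (0.064 in the check on contact means), so the report should then say that the level is approximate.
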